3.4.1 Randomization Procedure

After screening and written informed consent procedures have been completed, all eligible research participants entering the study will complete baseline procedures. After baseline assessments are completed, participants will be randomized into one of two groups: 1) DSME + Mind-STRIDE (the experimental group), or 2) DSME-Alone (usual care). The study statistician will perform the randomization process using statistical software with a random-number generator to create a list of group assignments before study recruitment begins. Randomization will occur in blocks of 4 or 6, and the group assignments will be created based on the specific number of expected eligible participants.

3.5 Description of Usual Care and Experimental Conditions

Participants in both conditions will continue their usual diabetes care as per their diabetes care providers. They will self-monitor their blood glucose according to instructions provided by their diabetes care providers, and will transmit data from their home blood glucose meters using standard VA issued Home Tele-Health equipment that is available and offered to all patients.

3.5.1 Usual Care Condition (DSME-Alone)

Patients randomized to the Usual Care Condition (DSME-Alone) will receive the standard 3-hour DSME class that includes a didactic presentation, discussion, and interactive activities using a booklet and power point slides covering the following topics:

- a) An overview of diabetes pathophysiology, HbA1c, major elements of DSM; distinguishing between T1DM and T2DM
- b) Eating Healthy - identifying nutrients, reading food labels, choosing healthy portion sizes
 - Activity: "My Healthy Eating Plan" - creating a personal eating plan
- c) Being Active- Being safe while make physical activity a regular part of your day, sample walking schedules
 - "My Activity Lifestyle Plan: getting started" -setting goals for daily activity
- d) Monitoring- Glucose testing tips; managing hypoglycemia and hyperglycemia
- e) Medications-Tips for taking medication safely; diabetes oral medications, classes and actions; insulin use, action and storage, injection site selection, use of a syringe or pen
 - Activity: "Keep Track of Your Insulin Doses" - writing down insulin doses
- f) Sick Day Management- maintaining insulin regimen; knowing what to eat when you're sick, guidelines for short-term illness, when to call your Health Care Team, when and how to get care immediately
- g) Living well with Diabetes- care of your heart, kidneys, eyes, and feet; care of your emotional health and travel tips
 - 1. Activity: "Tracking Diabetes Health" – documenting recent lab results, goals, targets, recent exams, and vaccines.

Participants in the Usual Care (DSME-Alone) condition also receive a 30- minute booster with the staff dietitian in which basic self-management skills and goals from DSME class are reinforced.

3.5.2 Experimental Condition (DSME +Mind-STRIDE)

Participants randomized to the Experimental Condition (DSME +Mind-STRIDE) will receive the same 3-hour DSME group class (described above) plus the 1-hour Mind-STRIDE intervention delivered by the Study Interventions that includes the following topics and activities:

- a) Group discussion: exploring the stress of living with diabetes (5 minutes)
- b) Meditation practice: Being in your body, "Body Scan Technique" (10 minutes)
- c) Group activity ("the raisin-eating exercise"): promoting awareness and differentiation between thoughts, judgements, and sensory perceptions (5 minutes)
- d) Didactic presentation and group discussion of stress theory; stress and diabetes; responding vs. reacting to stressful situations (15 minutes)
- e) Mindful movement (chair yoga) (5 minutes)
- f) Didactic presentation of mindfulness and mindful approaches to diabetes self-management, (10 minutes)
- g) Group discussion: mindfulness in everyday life, mindful eating (5 minutes)
- h) Group activity: setting intentions/commitment for daily home mindfulness practice. Tablets are distributed. (5 minutes)

The DSME + Mind-STRIDE group will also receive one 30 minute Mind-STRIDE booster session with the Study Interventionist in addition to the DSME booster with the staff dietitian. The Mind-STRIDE booster consists of:

- a) 20 minutes of discussion/reinforcement of mindfulness concepts
- b) 10 minutes of guided mindfulness meditation practice

The DSME+ Mind-STRIDE group will be encouraged to engage in at least 15 minutes of home mindfulness practice 6 days per week consisting of:

- a) 15-minutes of mindful meditation practice
- b) One daily mindfulness activity (e.g. mindfully eating one meal)
- c) Real-time tracking of home meditation practice using *Mindfulness Coach*, a VA-developed and supported application (Figure 4).

Figure 4. VA Mindfulness Coach Application

d) Optional journaling to reflect the home practice experience answering the question “What did you notice?”

Participants have the option of using 3-pre-loaded audio recordings on the tablets that were created by the PI and [name] to guide their home practice and reinforce the guiding mindfulness principles taught during the intervention. Participants will also access the pre-loaded *Mindfulness Coach* application for additional home practice support and to document home meditation practice. Recorded materials will be downloaded at each research visit. None of the data stored on the tablets will contain identifiable information, and personal use of the tablets’ internet features will be blocked during the course of study

3.6 Variables and Measures

3.6.1 Quantitative Measures

Diabetes-Related Distress (DRD), the primary outcome, will be measured with the Problem Areas in Diabetes scale (PAID). The PAID questionnaire will also be used for Screening to determine inclusion criteria of moderate to high baseline DRD (PAID score >10). It comprises 20 items that describe common negative feelings associated with having diabetes e.g. “Feeling scared when you think about living with diabetes?”, “Not having a clear and concrete goal for your diabetes care?” that are answered on a 5-point Likert scale (“Not a problem” to “Serious problem”). Item scores are summed to provide a total score of emotional distress, scores range from 0-100, with higher scores denoting greater distress. Scores over 40 denote burn-out, while scores of 10 or less may reflect denial. The PAID scale has high internal reliability (Cronbach’s alpha >.90), and has shown effect sizes between 0.30 and 0.65 across different psychosocial, educational, and medical interventions.¹⁹

Mindfulness- Two validated measures, a multi-faceted measure, the Five Facet Mindfulness Questionnaire (FFMQ), and a one-dimensional measure, the Revised Cognitive and Affective Mindfulness Scale (CAMS-R), will measure mindfulness. The FFMQ and CAMS-R measures self-reported mindfulness differently and are being used to address the complexity of assessing the construct. Mindfulness will be measured as a secondary outcome for Aim1.

The 5-Facet Mindfulness Questionnaire (FFMQ) is a validated questionnaire consisting of 39 items on a 5-point Likert scale (“Never or Very rarely true” to “Very often or Always true”) based on a factor analytic study of 5-independently developed mindfulness questionnaires. It measures 5-facets representing elements of mindfulness: observing, which refers to noticing or attending to internal and external experiences, such as thoughts, sensations, emotions, sounds, sights, and smells; describing, which refers to the ability to describe one’s emotions and feelings; acting with awareness, which includes attending to one’s activities in the present moment; non-judging of inner experience, which refers to taking a non-evaluative attitude toward thoughts and feelings; and non-reactivity to inner experience, which includes allowing thoughts and feelings to come and go, without getting caught up in or carried away by them. Higher scores reflect greater levels of each factor. Each factor consists of 7 or 8 items. The five facets demonstrated adequate to good internal consistency (alpha ranging from 0.75 to 0.91) when tested in experienced meditators and non-meditators.⁷⁰

The Revised 12-item Cognitive and Affective Mindfulness Scale (CAMS-R) is a one-dimensional, 12-item inventory on a 4 point Likert scale (“Rarely/Not at all” to “Almost always”) that measures mindfulness during general daily occurrences on four components of mindfulness (i.e., attention, awareness, present-focus, and acceptance/non-judgment) and yields one total score. Higher scores denote greater mindfulness. The internal consistency of the CAMS-R in this sample is adequate (alpha= .76), and there is evidence of convergent and discriminant validity with concurrent measures of mindfulness, distress, well-being, emotion-regulation, and problem-solving approaches.⁷¹

Self-Efficacy will be measured with the Diabetes Self-Efficacy Scale (DSES). This self-administered questionnaire consists of 8-items on a 10 point Likert scale (1= *Not confident at all*; 10 = *Totally confident*) that measures self-efficacy in diabetes self-management activities, with higher score denoting greater diabetes self-efficacy. Content validity of the DSES was supported in a study of 186 subjects who completed a six-week community diabetes education and lifestyle program. The internal consistency reliability of this instrument is high (alpha=.83).⁷²

Diabetes Self-Management will be measured with the Self-Care Inventory Revised (SCI-R), a psychometrically sound 15-item self-administered survey that measures perceived adherence to recommended diabetes self-care behaviors of adults with T1DM and T2DM. Higher scores reflect greater diabetes self-management behaviors. It was tested in 3 separate studies in 554 adults with diabetes and found to have high internal consistency ($r=.63$). Its construct validity is supported by correlations with diabetes distress ($r=-.36$); self-esteem ($r=.25$) self-efficacy ($r=.47$), depression ($r=-.22$) anxiety ($r=-.24$) and HbA1c ($r=-.37$). Responsiveness analysis showed SCI-R scores improved with diabetes psycho-education with a medium effect size of 0.62 and a Guyatt responsiveness statistic of 0.85.⁷³

Glycemic control, i.e., HbA1c, the secondary (distal) metabolic outcome, will be assessed at each time point: T1, T2, and T3. All tests will be performed at VAPHS laboratories according to National Glyco-hemoglobin Standardization Program approved methods using high performance liquid chromatography (Tosoh Bioscience South San Francisco, CA).

Potential Covariates

Frequency and duration of mindfulness practice will be measured by participant entries using the VA Mindfulness Coach Application. This application is a user -friendly method for timing and tracking meditation practice (in minutes) that also includes guided meditations and formats for personalized meditation sounds and music.

Depression will be measured with the Patient Health Questionnaire (PHQ-9), a widely used brief 9-item instrument adapted from the longer PHQ for measuring the severity of symptoms of depression over the past two weeks. The assessment can be administered repeatedly, and can reflect improvement or worsening of symptoms. Response options are on a 4-point Likert scale (0="Not at all"; 3="Nearly every day"). Item 9 assesses for the presence and duration of suicidal ideation. A tenth non-scored question assigns weight to the degree to which depressive problems have affected the patient's level of function. The validity of PHQ-9 was tested in 15 studies in primary care and obstetrical clinics. PHQ scores ≥ 10 had a sensitivity of 88% and a specificity of 88% for major depression. PHQ-9 scores of 5, 10, 15 and 20 represent mild, moderate and moderately severe and severe depression respectively. We will follow VAPHS policy for suicide assessment/ crisis treatment for those with positive responses to item 9.⁷⁴

Post-Traumatic Stress will be measured with the psychometrically valid PTSD checklist for DSM-5 (PCL-5) a 20-item self-report measure that assesses the 20 DSM-5 symptoms of PTSD over the past month on a scale of 0 ("Not at all") to 4 ("Extremely"). Higher scores reflect greater PTSD. Evidence for the PCL for DSM-4 suggests that a 5-10 point change represents reliable change (i.e., change not due to chance) and a 10-20 point change represents clinically significant change. Change scores for PCL-5 are currently being determined. It is expected that reliable and clinically meaningful change will be in a similar range, but is subject to further validation.

Social Support will be measured with The Support Attitudes Sub-scale of the Diabetes Care Profile (DCP), a self-administered questionnaire that assesses social and psychological factors related to diabetes and its treatment. The DCP Support Attitudes Subscale consists of 4 questions: one single answer multiple-choice question and three other questions, each with 6 sub-questions, on a 5-point Likert scale ("Strongly disagree" to "Strongly agree"). Higher subscale scores reflect greater social support or social support needs. Cronbach's alpha for the Support Attitudes Subscale was .69 and .73 demonstrating reliability. The Social Attitudes Subscale is significantly ($p \leq .01$) correlated with The Social Provisions Scale ($r=.51$), CES depression scale ($r=-.35$) and the Happiness and Satisfaction scale ($r=.25$) demonstrating concurrent validity.⁷⁵

Comorbidity will be measured with the Charlson Self-Report Comorbidity Index, a reproducible and valid 16-item self-report questionnaire that includes items corresponding to each element of the medical record-based Charlson index, a commonly used comorbidity risk assessment. Higher scores reflect greater comorbidity. The questionnaire was tested in 170 hospital inpatients and compared to Charlson scores abstracted from these patients' medical records. Responses are dichotomous yes or no answers to the questions, "Has a doctor or other health care provider ever told you that you have..." Test-retest reliability assessed with the intra-class correlation coefficient was 0.91 for the questionnaire and 0.92 for the chart-based Charlson index. Spearman

correlation between these two measures was 0.63. The correlation between comorbidity measures was weaker in less educated patients, but overall offers practical advantages over intensive medical-record based assessments particularly for use as a screening tool. Scores above 75 are considered to represent high comorbidity.⁷⁶

Demographic characteristics will be measured with an investigator-created questionnaire developed specifically for this study and includes age, race, ethnicity, duration of diabetes, diabetes medications, changes to diabetes medications within the past 60 days, marital status, occupation, employment status, and highest level of education completed.

3.6.2 Data Collection

A summary of the timeline for data collection procedures appears in Table 5.

Table 5. Variables and Measures Timeline

Variables	Measures*	Screen	T1 (Pre)	Week 4 Booster	T2 (Week 12)	15-week Interview	T3 (Week 24)
Anthropomorphic measures	BMI (kg/M ²)		X		X		X
Blood Pressure	BP mm/Hg		X		X		X
Co-Morbidity	Charlson Self-Report index		X				
Demographics	Investigator Questionnaire		X				
Depression	PHQ-9		X		X		X
Diabetes Self-Efficacy	DSES		X		X		X
Diabetes Self-Management	SCI-R		X		X		X
DRD	PAID	X			X		X
Glycemic Control	HbA1c	X			X		X
Mindfulness	FFMQ, CAMS-R		X		X		X
PTSD	PLC-5		X		X		X
Satisfaction (DSME+ Mind-STRIDE only)	PSQ			X			
Social Support	DCP Support Attitudes Scale		X		X		X
Veteran Satisfaction and Experience with Mind-STRIDE (Experimental group sub-sample)	Qualitative Telephone Interview					X	

3.6.3 Participant Burden

The total estimated time it will take to participate in the study beyond that of usual care over the 24 week study duration for the DSME-Alone group is approximately 5-hours, and 30-hours for the DSME+ Mind-STRIDE group, with the bulk of time occurring during the first 6 weeks for screening, assessments, and class and booster attendance. This time estimate for the usual care DSME-Alone group includes: screening and informed consent processes (2 hours) and three 1-hour assessments (3 hours). The time estimate for the experimental group also includes the (1 hour) Mind-STRIDE intervention, the 4-week Mind-STRIDE booster session (30-minutes), home mindfulness practice (~24 hours). Journaling with each home practice session is encouraged, but is optional and will depend on each individual. Journaling can take as little as 1 minute or up to several minutes (~3 hours). Qualitative telephone interviews will also be conducted in a subset of 25 purposively sampled experimental group participants (40 –minutes).

3.7 Data Analysis

3.7.1 General Analytic Approach for Aim 1:

Aim 1: To compare the effects of the intervention (DSME+ Mind-STRIDE) with those of usual care (DSME-alone) on diabetes distress, diabetes self-efficacy, and DSM in military Veterans over time.

Hypotheses. From baseline to 24-week post-intervention, DSME+ Mind-STRIDE compared to DSME-Alone will:

1. Significantly reduce DRD (primary outcome)
2. Significantly increase mindfulness, diabetes self-efficacy and diabetes self-management (secondary behavioral outcomes)
3. Significantly decrease HbA1c (distal metabolic outcome)

Independent variable: The Mind-STRIDE intervention, which includes mindfulness stress reduction, mindfulness meditation training and home practice.

Dependent variables: The primary outcome on which the analysis is powered is DRD measured by the PAID scale. Secondary outcomes include diabetes self-efficacy, diabetes self-management, mindfulness, and glycemic control, measured by HbA1c.

Analysis: To assess whether there are group differences over time, we will use separate linear (or non-linear depending on outcome) mixed models for each outcome (diabetes distress, primary), diabetes self-efficacy, diabetes self-management, mindfulness and glycemic control (secondary) for 3 time points (baseline, 12 weeks post-intervention, and 24 weeks post-intervention). The base model will include fixed effects for treatment group DSME+ Mind-STRIDE, DSME-Alone group, time, and the interaction between treatment group and time. To the extent possible, post-hoc analyses to explore the possible relationships between mindfulness and diabetes-related distress (as well as the interaction between them) on the distal secondary outcome, glycemic control will be performed.

Power analysis: Power calculations for Aim 1, hypothesis 1 of this study were based on a repeated measures design (2 sided $\alpha = .05$) with 2 treatment groups (DSME+ Mind-STRIDE; DSME-Alone) and 3 time points (baseline, 12 weeks post intervention, 24 weeks post-intervention). We computed sample size estimates that were powered to detect an overall treatment group difference in DRD (PAID scale score) as well as a treatment group difference over time (interaction between treatment group and time). Based on our pilot work, a medium effect size ($d = .6$) gives a clinically meaningful change in PAID score. Using a medium ($d = .5$) effect size, and estimates of the correlations between observations on the same subject of $r = .5$, powering at 80% gives a sample size estimate of 86 (~43 per group). To account for possible clustering due to the randomization occurring in groups of $n = 5$ participants, the required total sample size (86) was inflated by a factor of $(1 + (5-1) * p)$, where p is the intra-cluster correlation coefficient.^{78, 79} A conservative estimate of the intra-cluster correlation of $p = 0.05$, gives an increased sample size of 104 (~52 per group). To ensure a sample of 104 at study completion, 126 Veterans will need to be recruited over the 2-year study period. This number of 126 Veterans is approximately 20% of the usual number of Veterans referred for DSME over two years and is within what is considered reasonable to recruit based on our pilot data. Sample size estimates were computed in Stata Statistical Software: Release 12 (College Station, TX: StataCorp LP; 2011).

[name] PhD, Associate Professor of Biostatistics at the University of Pittsburgh Graduate School of Public Health, will oversee statistical analysis for Aim 1. Analyses for Aim 1 will be performed using Stata statistical software. Diabetes distress (the primary outcome) and secondary outcomes (mindfulness diabetes self-efficacy, diabetes self-management, and HbA1c) will be assessed for normality and appropriate data transformations will be used if necessary. Descriptive statistics will be computed to determine central tendency, data sparseness, and existence of outliers for all other continuous variables. Frequency distributions will be generated for categorical variables to identify data sparseness, and categories with small frequencies will be merged when appropriate. In addition, we will consider categorization of continuous predictors if the distributions are skewed or violate assumptions of linearity. Differences in covariates by treatment group will be tested using chi-square (or Fisher's exact) statistics for categorical variables and t-test (or Mann-Whitney) for continuous variables. Graphical procedures will be used to assess simple change in the outcomes over time. For the main analyses for Aim 1, we will test study hypotheses by using linear mixed models (or non-linear

mixed models where appropriate), which account for repeated measures and assess change over time (baseline, 12 weeks, 24 weeks). The linear mixed model allows for missing data if data are missing at random. Demographic variables with a univariate association with the outcome ($p < 0.10$) or differed by treatment group at baseline ($p < 0.05$) will be considered for inclusion in a multivariate model. Covariates will be retained in the final multivariable models if significant at $p < 0.05$. All tests will be two-sided. All analyses will be conducted as intent-to-treat analyses and include all patients in the groups to which they were randomized, regardless of adherence and/or subsequent withdrawal.

Missing Data. We will review all assessments for completeness during the session in which it is collected to attempt to minimize missing data for Aim 1. We will attempt to assess the missing data mechanism for missing data due to lost to follow-up or withdrawal. If there are significant differences in baseline variables between those subjects that have complete outcome data and those that do not, we will adjust for those covariates as part of the modeling.⁸⁰ If no systematic differences are found or if the missing data is intermittent, the missingness will be handled as part of the regression modeling. Using linear mixed linear models allows the use of all available data, including data from those who are missing one or more of the assessments. We will also perform completers only analyses and see if these differ compared to the modeling using all of the available data to assess sensitivity to the missingness.

3.7.2 General Analytic Approach for Aim 2

Aim 2: To identify Veteran satisfaction and experiences with DSME +Mind-STRIDE.

We will use Convergent Parallel Design (Figure 5) to develop a more complete understanding of the research questions by obtaining different but complementary quantitative (Aim 1) and qualitative (Aim 2) data.⁸¹ Collecting and analyzing two independent strands of data at the same time in a single phase will enable us to prioritize the methods equally while keeping the data analysis independent. We will then mix the results at the point of interface, looking for convergence, divergence, contradictions or relationships of the two sources of data that will inform the overall interpretation of study results.

[figure not shown]

Figure 5. Convergent Parallel Design

Specifically, audio recordings will be made using digital recording devices that are Federal Information Processing Standard (FIPS) 140-2 compliant. All interviews will be audio-recorded using a VAPHS-approved encrypted digital recorder. Audio recordings will be protected per VAPHS policy. Trained interviewers will conduct semi-structured interviews developed specifically to address Qualitative-Aim 2. A standardized telephone interview guide (Appendix 4) will ensure sufficient uniformity across the interviews in topics covered and in sequencing to allow comparisons. As further interview preparation, we will pilot test the interview guides with 2-4 patients. The pilot will assist in determining whether refinement or modification of questions is needed, allowing us to make necessary revisions.⁸² If the interview guides are not significantly modified as a result of the pilot, the information gathered from the people who participated in the pilot will be added to the information obtained from participants in the full study.

The semi-structured interview guide will contain open-ended questions (including clarifying questions) that also will provide the flexibility to explore topics and elicit patient experiences in greater depth—with probing questions according to varied patient experiences. Participant interviews will be aimed at exploring Veteran satisfaction and experiences with the Mind-STRIDE class provided within DSME. The interview will also explore their experience with mindfulness training and home mindfulness practice in general and relative to diabetes management. When possible, DSME+ Mind-STRIDE participants will be asked additional questions guided by observations recorded in their journals to enable more contextual exploration of their mindfulness experience. The interviews will (1) provide detailed "thick" descriptions about Veteran experiences with Mind-STRIDE and mindfulness practice that do not rely on predefined quantitative study instrument categories,⁸³ and (2) provide patients the opportunity to elaborate about moment to moment experiences associated with mindfulness practice. The interviews will take approximately 20-30 minutes and will be audio-recorded and transcribed verbatim by a trained transcriptionist at the Center for Health Equity Research and Promotion

(CHERP). Results of interviews will be summarized into topics discussed, as well as the range of thematic issues, concerns, or foci of the patient. We will also record the frequencies of topics and themes that emerge. Recordings will be stored according to VA information security specifications.

A sub-sample of 25 DSME+ Mind-STRIDE participants will be selected for the interviews by purposive sampling with maximum variation in order to represent a wide range of age groups, race/ethnicity, and severity/type of diabetes.⁸⁴ Verbatim transcripts from interviews with 25 DSME+ Mind-STRIDE participants are sufficient for thematic saturation—which requires a minimum of 12-20 participants of each “type.”⁸⁵ The transcribed data will be de-identified and imported into ATLAS.ti (Scientific Software, Berlin, Germany) for data management and analysis.⁸⁶ Two coders are standard and necessary in qualitative research to ensure reliability of the coding scheme.⁸⁷ [name] will train the coders (existing study staff) to develop qualitative codebooks for the patient interviews.

[name] PhD, Research Health Scientist and CHERP Core Investigator at VAPHS, will oversee qualitative data analysis for Aim 2. Using a modified grounded theory approach for data analysis, trained coders will use the constant comparative method to compare newly gathered data with previously collected data to develop categories of responses.⁸⁴ Initially, the two coders will employ an iterative process of close readings and discussion of a sample of interview transcripts to identify emergent concepts, categories, themes and relationships in the data and develop an initial set of codes to be applied to subsequent transcripts. The broad areas of foci will include Veteran satisfaction and experiences of mindfulness training and practice. As the coders examine more transcripts, they will refine their coding sub-categories and develop a coding scheme. In the case of disagreements, they will further develop rules to distinguish codes. If necessary, the coders will consult with the research team to refine the criteria. Both coders will then each code 100% of the transcripts independently.⁸⁷ We will use a system of audit trails to document the creation of all codes and Kappa statistics will be computed to assess inter-coder agreement. The coders will meet and process any differences in coding for each interview until agreement is achieved. If the two coders discussed a discrepancy and are unable to come to a consensus, a resolution will be reached with [name] and the PI’s adjudication. The codes determined through this consensus process will be recorded in a master file, which will become the basis for the final analysis. This process of coding will maintain narrative coherence with inter-coder reliability kappa scores > 0.75.⁸⁸

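### The plan does not say which PAID test decides hypothesis 1 and gives no power for week 24, and its base model loses precision by leaving baseline PAID free by arm

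*Combined protocol and SAP*

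**What the plan says.** Section 3.7.1 introduces the hypotheses with the words "From baseline to 24-week post-intervention, DSME+ Mind-STRIDE compared to DSME-Alone will" and lists reduction of diabetes-related distress, measured by PAID, first. The analysis is a mixed model on baseline, week 12 and week 24: "The base model will include fixed effects for treatment group DSME+ Mind-STRIDE, DSME-Alone group, time, and the interaction between treatment group and time". Later text in the section describes these models as ones "which account for repeated measures and assess change over time".

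The power paragraph says the sample size was "powered to detect an overall treatment group difference in DRD (PAID scale score) as well as a treatment group difference over time", the latter being the interaction. With d = 0.5 and within-person correlation 0.5, "powering at 80% gives a sample size estimate of 86". A factor of 1 + (5 − 1) × 0.05 = 1.20 raises this to 104 completers, and 126 are to be recruited. The same paragraph calls d = 0.6 clinically meaningful.

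On timing, section 3.4.1 says: "After baseline assessments are completed, participants will be randomized into one of two groups". Section 3.6.1 adds: "The PAID questionnaire will also be used for Screening to determine inclusion criteria of moderate to high baseline DRD". Table 5 marks PAID at Screen, week 12 and week 24, but not at T1. Candidate covariates are "Demographic variables with a univariate association with the outcome" or that differ by arm at baseline, baseline variables related to missing outcomes (Missing Data paragraph), and medication (section 3.9).

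**The concern.** The planned model yields several candidate tests of hypothesis 1: the group term, the 2-df interaction, and separate 1-df terms for weeks 12 and 24. The wording leans towards group-by-time, and week-24 change is the natural reading of the hypothesis. However, no sentence makes any one of these the deciding test, so the choice could be made after the data are seen. Nor can a reader tell what power the trial has for the week-24 question.

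The second issue is efficiency. PAID is measured before randomisation, so both arms have the same expected baseline. The base model nevertheless estimates a separate baseline mean for each arm and measures the week-24 effect from it. None of the permitted covariates guarantees that baseline PAID enters the model.

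**Working it through.** **Inputs from section 3.7.1:** two-sided 0.05; d = 0.5 (and 0.6); r = 0.5; 86 in total; design effect 1.20; 104 completers. **Assumed here:** r = 0.3 and 0.7; a ratio k of baseline SD to week-24 SD of 1.0, 0.9 or 0.8; complete data; d in week-24 SD units. Power is from the noncentral t with noncentrality d × √(n / 2V), where n is per group and V is the variance factor of the contrast.

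**1. The plan's 86.** For the mean of three visits, V = (1 + 2r)/3 = 2/3. At n = 43 the noncentrality is 0.5 × √(43/1.333) = 2.84 and power is 80.1%; at n = 42 it is 79.2%. So 86 reproduces, and 86 × 1.20 = 103.2, rounded up to 104. One of the three visits averaged precedes randomisation.

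**2. A week-24 contrast.**
- Baseline free by arm: V = k² + 1 − 2rk = 1.00 at k = 1, r = 0.5. This needs 64 per group for 80%.
- Common baseline mean, or baseline as covariate: V = 1 − r² = 0.75. This needs 49 per group.

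A generalised least squares check of the two three-visit models gives the same factors, 1.00 and 0.75. Neither requirement is 43.

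**3. The interaction.** Under the convention f = d/2 = 0.25, the 2-df test needs 28 in total. With d = 0.5 at both follow-up visits it needs 118. The plan gives no pattern of effect across visits, so its power cannot be settled from the documents.

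**4. Precision given up.** The share of the week-24 change variance removed by adjustment is (k − r)² / (k² + 1 − 2rk):

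| SD ratio k | r = 0.3 | r = 0.5 | r = 0.7 |
|---|---|---|---|
| 1.0 | 35% | 25% | 15% |
| 0.9 | 28% | 18% | 7% |
| 0.8 | 22% | 11% | 2% |

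A ratio below 1 is plausible because entry requires PAID above 10.

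**5. Week-24 power at the planned size.** Effective n = 104 / 1.20 / 2 = 43.3 per group.
- d = 0.5, r = 0.5, adjusted: noncentrality 0.5 × √(43.3/1.5) = 2.69, power about 76%. At r = 0.3 it is 67%; at r = 0.7 it is 90%.
- d = 0.5, r = 0.5, unadjusted, k = 1: noncentrality 0.5 × √(43.3/2) = 2.33, power about 63%. With k = 0.9 (V = 0.91) it is 67%; with k = 0.8 (V = 0.84) it is 71%.
- d = 0.6, r = 0.5: about 89% adjusted and 79% unadjusted with k = 1.

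The adjusted figures do not depend on k.

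**The case against.** The plan already fixes the outcome, the comparison, the interval and a model containing group-by-time, and the power paragraph names that interaction. A reader might infer that the power statement and the hypothesis test concern wholly different quantities. The documents do not support that, because the interaction is one of the two stated targets. Nor do they support reading 86 as an arithmetic error: it reproduces for the overall target and may simply be the larger of the two requirements. A claim that the interaction is under-powered would also fail, since step 3 gives either answer depending on an unstated effect pattern. What remains is narrower: two targets, neither designated as deciding, and no week-24 power.

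A group, time and interaction model with baseline as a response is also a valid analysis. That is correct: the free baseline does not bias the comparison, and the gain from adjustment is small if r is high and the baseline SD is low. Still, the gain uses data already planned, and adjustment does not reduce precision in any scenario shown.

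Finally, PAID is marked at Screen rather than T1. Screening still precedes randomisation, so a common baseline mean remains justified.

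**Conclusion.** The point holds in two parts. First, no available text designates the deciding PAID test or states power for week 24, and the stated sample size belongs to a test averaged over three visits. Second, the base model is unbiased but less precise than it could be for week 24. With equal SDs and r = 0.5, adjustment is worth about 13 percentage points of power at d = 0.5 (63% to 76%) and about 10 at d = 0.6 (79% to 89%). These gains rest on the plan's r and design effect and on equal SDs at baseline and week 24; at d = 0.5 and an assumed SD ratio of 0.8 the gain is about 5 points (71% to 76%). Some pages were not available for review, so a designation there cannot be excluded. This should be changed, but it does not invalidate the design.

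**What to change.** In section 3.7.1:

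1. Fit the planned mixed model for PAID with a common baseline mean for both arms (or baseline PAID as a covariate), time, and group terms at weeks 12 and 24. State that baseline is the pre-randomisation PAID marked at Screen in Table 5.
2. Name the 1-df group difference at week 24, two-sided 0.05, as the primary test. Make week 12 and the overall effect secondary.
3. Restate power for that test using the t-based figures in step 5 above, at both d = 0.5 and d = 0.6 and with the range over r. If the unadjusted figure is shown, say that it assumes equal SDs.

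The cost is SAP wording and one power statement, with no new measurement or visit. The downside is that the stated 80% becomes about 76% at d = 0.5. Holding 80% there would take 98 × 1.20 = 117.6, so 118 completers, or 118 × 126/104 = 143 recruits at the plan's implied loss. That is not proposed; restating the figure is sufficient.
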